NCT01700959 - MIND

St. Jude

MIND

Initial version, dated: May 23, 2012 (resubmitted to CT-SCR 08-06-2012), (IRB Approved: 09-27-12)

Activation Date:

Amendment 1.0, dated: October 22, 2012 (IRB Approved: 12-20-12)

Activation Date: January 24, 2013

Amendment 2.0, dated: March 1, 2013 (IRB Approved: 05-28-13)

Activation Date: June 4, 2013

Revision 2.1, dated: September 9, 2013 (IRB Approved: 10-29-13)

Amendment 3.0, dated: June 16, 2014 (IRB Approved: 09-18-14)

Activation Date: September 18, 2014

Amendment 4.0, dated: January 26, 2015 (IRB Approved: 03-10-15)

Activation Date: March 11, 2015

Revision 4.1, dated: October 27, 2015 (IRB Approved: 12-2-15)

Revision 4.2, dated: March 16, 2016 (IRB Approved: 03-29-16)

Revision 4.3, dated: September 20, 2016 (IRB Approved: 10-11-16)

Activation date: October 17, 2016

**MELATONIN INTERVENTION FOR NEUROCOGNITIVE DEFICITS IN THE
ST. JUDE LIFETIME COHORT**

Principal Investigator

[name]

Epidemiology and Cancer Control

St. Jude Children's Research Hospital
[name]
[name]
[contact]

Protocol Summary

Protocol MNEMONIC and Title: MIND - Melatonin Intervention for Neurocognitive Deficits in the St. Jude Lifetime Cohort
Principal Investigator: [name].
IND Holder: N/A
Brief Overview: This study is a randomized double-blind placebo controlled trial of time release melatonin for adult survivors of childhood cancer who demonstrate impaired neurocognitive functioning and/or delayed sleep onset latency. The sample will be stratified to generate three mutually exclusive cohorts. Cohort 1: neurocognitive impairment without delayed sleep onset latency; Cohort 2: neurocognitive impairment with delayed sleep onset latency; Cohort 3: delayed sleep onset without neurocognitive impairment. Within each group, participants will be randomly allocated to either melatonin or placebo for a 6-month trial. Participants will take 3mg of time release melatonin or placebo orally each night prior to initiating sleep onset. Baseline and follow-up evaluations will be completed to determine the effects of melatonin on specific neurocognitive processes and sleep parameters.
Intervention: Survivors who previously underwent neurocognitive evaluation as part of the SJLIFE study, as well as survivors who are eligible for future neurocognitive evaluation through SJLIFE will be recruited. Initial eligibility will be determined via review of previous neurocognitive assessment data and telephone screening. Interested survivors meeting the pre-screen criteria will complete standardized sleep measures at their baseline visit. Baseline neurocognitive assessments will occur as part of the SJLIFE study. Neurocognitive assessments will be administered again at 6 months. Subjective and objective sleep measures including actigraphy will be assessed at baseline, 3 months, and 6 months. Correlative psychosocial measures of health-related quality of life and psychological distress will be completed at baseline as part of the SJLIFE study and following 6 months on treatment. Serum melatonin will be collected at baseline and 6 month follow-up.
Brief Outline of Treatment Plan: Participants will take a fixed 3 mg oral dose of time release melatonin or placebo once per day 1-2 hours before initiating sleep onset for a 6 month period. Participants will be called biweekly throughout the intervention to monitor treatment adherence, side effects, and adverse events.

Protocol MNEMONIC and Title: MIND - Melatonin Intervention for Neurocognitive Deficits in the St. Jude Lifetime Cohort

Primary Objective:

To examine the efficacy of melatonin treatment on neurocognitive functioning in adult survivors of childhood cancer.

Responsible Investigator: [name] and [name]

Secondary Objectives:

To evaluate the efficacy of melatonin treatment on delayed sleep onset latency in long-term childhood cancer survivors.

To investigate whether improvement in sleep onset latency due to melatonin treatment is associated with neurocognitive improvement in long-term childhood cancer survivors.

Responsible Investigators: [name] and [name]

Exploratory Objective:

To explore the association between endogenous melatonin levels and improvement in sleep onset latency.

To explore the association between sleep quality and health-related quality of life and distress.

Responsible Investigators: [name] and [name]

Estimated date for completion of data collection: [REDACTED]

Protocol MNEMONIC and Title: MIND - Melatonin Intervention for Neurocognitive Deficits in the St. Jude Lifetime Cohort

Hypotheses/Estimates:

- **Hypothesis 1:** Long-term survivors of childhood cancer with documented baseline neurocognitive deficits (Cohorts 1 and 2) in attention, memory, and/or executive functioning, randomized to the melatonin treatment arm, will demonstrate improved neurocognitive performance following six months of treatment compared to those randomized to placebo.
- **Hypothesis 2:** Long-term survivors of childhood cancer with delayed sleep onset latency at baseline (Cohorts 2 and 3), randomized to the melatonin treatment arm, will demonstrate improved sleep onset latency following 6 months of treatment compared to the placebo groups.
- **Hypothesis 3:** Improvement in sleep onset latency with melatonin treatment will result in improved neurocognitive performance in long-term childhood cancer survivors who have both comorbid sleep onset latency and neurocognitive deficits at baseline (Cohort 2).
- **Exploratory Hypothesis 1:** Improvement in sleep onset latency following melatonin treatment will be independent of baseline endogenous melatonin levels.
- **Exploratory Hypothesis 2:** Improved sleep quality will be associated with decreased psychological distress and enhanced quality of life.

Criteria for Evaluation:

Three domains of neurocognition will be examined as primary study outcomes 1) attention, 2) memory, and 3) executive functioning. Sleep parameters to be assessed include objective and subjective measures. Correlative psychosocial measures of health-related quality of life and psychological distress will be evaluated. Treatment adherence and side effects will be monitored.

Study Design: Prospective randomized, double-blind, placebo-controlled study

Protocol MNEMONIC and Title: MIND - Melatonin Intervention for Neurocognitive Deficits in the St. Jude Lifetime Cohort

Study Population:

Inclusion Criteria:

- 1) Previously treated at SJCRH and a participant in St Jude Life.
- 2) Is 10 or more years from diagnosis
- 3) FSIQ score > 79
- 4) \geq 18 years of age
- 5) Able to speak and understand the English language
- 6) **Cohort 1 participant:**
 - a. Has neurocognitive impairment defined as performance on at least one measure of attention, memory, and/or executive functioning \leq 10th percentile.
 - b. Is absent of delayed sleep onset latency defined as an inability to fall asleep within 30 minutes $<$ once a week during the past month.
- Cohort 2 participant:**
 - a. Has neurocognitive impairment defined as performance on at least one measure of attention, memory, and/or executive functioning \leq 10th percentile.
 - b. Has delayed sleep onset latency defined as self-report of an inability to fall asleep within 30 minutes \geq once a week during the past month.
- Cohort 3 participant:**
 - a. Is absent of neurocognitive impairment defined as performance $>$ 10th percentile on all six measures of attention, memory, and executive functioning.
 - b. Has delayed sleep onset latency defined as self-report of an inability to fall asleep within 30 minutes \geq once a week during the past month.

Study Population:

Exclusion Criteria:

- 1) Known allergy to melatonin or any ingredients of the study product or placebo
- 2) Currently taking Melatonin
- 3) Known sleep apnea
- 4) Known medically treated sleep disorder (e.g. restless leg syndrome)
- 5) Known diabetes mellitus – insulin treated
- 6) Uncontrolled seizure disorder in the past 12 months
- 7) Reported current illicit drug or alcohol abuse or dependence
- 8) Reported current major psychiatric illness (i.e. schizophrenia, bipolar disorder)
- 9) Current treatment with:
 - a. Benzodiazepines or other CNS depressants
 - b. Fluvoxamine
 - c. Anticoagulants (e.g. Coumadin)
 - d. Immunosuppressant or corticosteroids
 - e. Nifedipine
- 10) Employed in a position that requires night work (i.e. 10pm to 6am)
- 11) Females who are pregnant or lactating/nursing
- 12) History of neurologic event unrelated to cancer or its treatment
- 13) Sensory impairment (vision, hearing) that prohibits completion of neurocognitive examination

Protocol MNEMONIC and Title: MIND - Melatonin Intervention for Neurocognitive Deficits in the St. Jude Lifetime Cohort

Sample Size: Targeted enrollment 987 and expected evaluable 395 research participants

- Cohort 1 = 131
- Cohort 2 = 131
- Cohort 3 = 133

Randomization:

Participants in each cohort will be randomized 1:1 to receive time release melatonin 3 mg or placebo daily for 6 months.

Data Analyses:

Primary Aim: The primary aim of this study is to determine the difference between changes in neurocognitive functioning from baseline to the 6 month follow-up in adult survivors of childhood cancer who are randomized to receive melatonin compared to those randomized to receive placebo. We hypothesize that survivors randomized to the melatonin group will have a greater improvement in neurocognitive functioning than those randomized to the placebo group. We have identified six neurocognitive domains in which the marginal impairment rate is >15% in the SJLIFE cohort. Normalized Z-scores ($M=0$, $SD=1$) are available for each domain and survivors who score at or below the 10th percentile will be classified as impaired on that specific domain. The lowest test-retest correlation coefficient for the neurocognitive measures has been observed to be 0.60. Then, assuming the difference in the Z-scores to be normally distributed but assuming (conservatively) the variance to be 1, we need outcome data for 131 survivors between the melatonin and placebo arms in Cohorts 1 and Group 2 to detect an improvement of .66 units (in standardized scale, considered to be clinically meaningful) with 80% power with type I error control $\alpha=0.05/6=0.0083$ to adjust for multiplicity of 6 tests for each subscale. The analysis for Aim 1 will be completed using a two-sample t-test. Assuming an attrition and loss to follow up of 25%, we plan to enroll 987 survivors (Cohort 1=328; Cohort 2=328; Cohort 3=331).

Protocol MNEMONIC and Title: MIND - Melatonin Intervention for Neurocognitive Deficits in the St. Jude Lifetime Cohort

Secondary Aim 1: The primary interest of secondary aim one is to assess the efficacy of melatonin on delayed sleep onset latency in adult survivors of childhood cancer, which will be evaluated in Cohorts 2 and 3. We hypothesize that survivors randomized to the melatonin treatment arm will evidence a greater reduction in sleep onset latency compared to survivors randomized to placebo. The CCSS cohort mean and SD for sleep onset latency among participants with delayed sleep onset latency (i.e. SOL \geq 30 minutes) is 46.2 and 27.7 minutes, respectively. The test-retest correlation for sleep onset latency from the PSQI has been observed to be in the range of 0.70. Following the justification set forth in the Primary Aim, and assuming the SD to be 27.7, we will need outcome data for 131 survivors in Cohort 2 and 133 in Cohort 3 between the melatonin and placebo arms for these Cohorts to see an improvement of 15 minutes in sleep onset latency with 80% power with type I error control $\alpha=0.05$. The analysis for Aim 2 will be completed using a two-sample t-test.

Secondary Aim 2: The aim of this objective is to investigate the association between sleep onset latency and specific neurocognitive processes [Cohort 2]. We hypothesize that decreased sleep onset latency following 6 months of melatonin treatment will be associated with improved neurocognitive performance. We will need outcome data for 131 survivors in Cohort 2 [66 randomized to melatonin, 65 randomized to placebo] so that we will have 80% power to detect a correlation of at least 0.25 between reduced sleep onset latency and improved neurocognitive performance with type 1 error control $\alpha=0.05$.

Exploratory Aims: To explore the association between endogenous melatonin levels and improvement in sleep onset latency. To explore the association between sleep quality and psychological distress and health related quality of life.

Primary Anticipated Completion Date: [REDACTED]

Anticipated Study Completion Date: [REDACTED]

Timeframe for Primary Outcome Measure: Approximately 6 months

Data Management: Data will be managed by the Neuropsychology Research Team and the Clinical and Survey Research Center in the Department of Epidemiology and Cancer Control and the Department of Nursing Research. Statistical analysis will be provided by the Biostatistics Department at St. Jude Children's Research Hospital.

Human Subjects:

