There are 10 subscales on which a survivor could be impaired and, out of 10 such subscales, we have identified six in which the marginal impairment rates were seen to be greater than 15%. There are normalized Z-scores available for each subscale and a survivor that falls below the 10% (≤ -1.3) is classified as impaired on that subscale. It is possible that a survivor could be impaired on more than one subscale but we will assess improvement in each subscale independently. Thus, we will have the Z-score corresponding to each of the subscales within at baseline and at follow-up visit. For simplicity, consider the first subscale. We don't expect to see any change in the Z-scores for the placebo arm but we do expect to see an improvement in the melatonin arm. Let Z_{1m}^1 and Z_{2m}^1 denote the Z-scores at baseline and follow-up time points for the first subscale on melatonin arm and let Z_{1p}^1 and Z_{2p}^1 denote the Z-scores at baseline and follow-up time points for the first subscale in the placebo arm. Let $Z_{DM}^1 = Z_{2m}^1 - Z_{1m}^1$ and $Z_{DP}^1 = Z_{2p}^1 - Z_{1p}^1$ denote the difference between the two time points in the two arms. Then our interest is in testing the null hypothesis $H_0: \mu_{Z_{DM}^1} = \mu_{Z_{DP}^1}$ vs $H_1: \mu_{Z_{DM}^1} \neq \mu_{Z_{DP}^1}$ i.e. the mean of the difference scores for the first subscale would be same for the two arms vs. they will be different. The lowest test-retest correlation coefficient for the neurocognitive measures has been observed to be 0.60. Then, assuming the difference in the Z-scores to be normally distributed but assuming (conservatively) the variance to be 1, we will need to randomize 131 survivors between the melatonin and placebo arm to detect an improvement of 0.66 units (in standardized scale, considered to be clinically meaningful) with 80% power with type I error control $\alpha=0.05/6=0.0083$ to adjust for multiplicity of 6 tests for each subscale. However, the sample size required to evaluate the secondary objective in cohorts 2 and 3 is 131 and 133, respectively, per cohort. Thus, we plan to enroll 131 research participants from Cohorts 1 and 2 and 133 research participants from Cohort 3.

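### The fixed 0.05/6 cut for the six primary subscales is valid but less efficient than Holm's step-down, which keeps the same error guarantee and adds 0 to about 9 points of per-subscale power at the planned effect, depending on how many subscales respond

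*Combined protocol and SAP*

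**What the plan says.** The Protocol Summary (Data Analyses, Primary Aim) and Section 11.0 (Primary Objective) set one significance level for every primary test: "type I error control $\alpha=0.05/6=0.0083$ to adjust for multiplicity of 6 tests for each subscale". The test is named in the Summary: "The analysis for Aim 1 will be completed using a two-sample t-test". Section 11.0 makes it two-sided, since the hypotheses are that "the mean of the difference scores for the first subscale would be same for the two arms vs. they will be different".

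Section 11.0 allows that a survivor may be impaired on several subscales, "but we will assess improvement in each subscale independently". It also has Cohorts 1 and 2 evaluated separately, so the family as written is six tests per cohort. Neither place gives a step-down, gatekeeping or other sequential rule. The level appears in a sample-size sentence, but it is the only multiplicity rule for the primary tests, so in practice it is the decision rule.

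**The concern.** Bonferroni compares all six p-values with 0.0083. Holm compares the smallest with 0.05/6. If that is significant it compares the next with 0.05/5, then 0.05/4, and so on up to 0.05, and stops at the first failure. Both rules hold the chance of any false claim within the family at or below 0.05, however the subscales are correlated. Holm's first threshold equals Bonferroni's and its later ones are looser, so over the same family it can never reject fewer.

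What is at stake is which subscales the trial can claim. Attention, memory and executive function are named as separate primary outcomes, with two subscales described under each in Section 4.1. If melatonin works broadly, the fixed cut will more often support a claim on only some of the subscales that respond.

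**Working it through.** **Inputs from the documents.** Difference in mean change 0.66; SD 1 ("assuming (conservatively) the variance to be 1"); 131 survivors with outcome data per cohort, randomized 1:1, so 66 and 65; two-sided pooled t-test; alpha 0.05/6 = 0.0083; stated power 80%.

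**Assumptions.** The number of subscales that truly shift by 0.66 (1 to 6) and the correlation between subscale change scores (0 to 0.8). Neither is given for the t-tests.

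**Step 1: the plan's own figure.**
- Noncentrality = 0.66 / √(1/66 + 1/65) = 0.66 / 0.1747 = 3.777.
- The critical value of t on 129 df at two-sided 0.0083 is 2.680.
- Noncentral-t power is 86.2%, not the stated 80%.
- For 80% power at 0.0083, N = 115 is enough (58 vs 57, 80.1%), or 116 with equal arms.
- N = 131 does give 80.3% at 0.05/12 = 0.0042. The size therefore fits an alpha also divided over the two cohorts. That is an inference from the arithmetic; the text does not say it.

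The baseline for the written rule at the written N is therefore 86%.

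**Step 2: Holm thresholds for six tests.** 0.05/6 = 0.0083, 0.05/5 = 0.0100, 0.05/4 = 0.0125, 0.05/3 = 0.0167, 0.05/2 = 0.0250, 0.05/1 = 0.0500.

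**Step 3: power per truly responding subscale, by simulation.** 66 vs 65, SD 1, gain 0.66, correlation 0.3:

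| Subscales responding | Bonferroni | Holm |
|---|---|---|
| 1 | 86% | 86% |
| 2 | 86% | 87% |
| 3 | 86% | 89% |
| 4 | 86% | 90% |
| 5 | 86% | 92% |
| 6 | 86% | 94% |

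With all six responding, Holm gives about 95% at correlation 0, 93% at 0.5 and 92% at 0.8.

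**Step 4: all, and at least one.**
- Chance of finding all six when all six respond: Bonferroni 0.862⁶ ≈ 41% at correlation 0, and 52% at 0.3. Holm gives about 79% and 81%.
- Chance of finding at least one true effect: the same to within about 0.1 point in every case. With all six responding at correlation 0.3 it is 99.8% under both rules.

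**Step 5: error control.** Holm's family-wise error stayed at or below 0.049 per cohort, and it never rejected fewer subscales than Bonferroni in any replicate.

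**Step 6: smaller gains.** With all six responding at correlation 0.3, a gain of 0.5 gives 57% to 69%, and a gain of 0.3 gives 17% to 20%.

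**Step 7: a family of 12.** At 0.05/12 and correlation 0.3, Bonferroni gives 80%. Holm over 12 gives about 93% if all 12 effects are real, 84% if three per cohort are, and 81% if one per cohort is. Holm over 12 is not uniformly better than the written 0.05/6. Suppose a cohort's smallest p-value is 0.006 and is also the smallest of the 12. It passes 0.0083 but fails Holm's first threshold of 0.0042.

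**The case against.** Bonferroni at 0.05/6 is pre-specified, conventional and valid, so no error has been shown. That stands, and it sets the weight of this point. It does not make the choice a matter of taste: over the same family, Holm gives the same guarantee and never does worse.

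A reader might infer that the plan's own effect implies a rise from 86% to about 94%. The documents do not support this without a condition. Section 11.0 takes the first subscale for simplicity, sizes a single test, and never says how many subscales will shift by 0.66. Its alternative count analysis does give all six the same improvement probability (12% vs 5%), so a broad effect is one of the sponsor's working models, but not for the t-tests. Entry to Cohorts 1 and 2 requires impairment on only one measure, so a mean shift of 0.66 on all six is the favourable end of the range. If one subscale responds, Holm adds nothing.

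A reader might also infer that the trial risks missing any benefit at all. It does not: Holm's first step is the Bonferroni test, so the chance of at least one finding hardly moves.

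The count analysis at alpha 0.05 also targets a broad effect. It gives one overall comparison and does not say which subscales respond, so it does not replace the per-subscale rule.

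Finally, Holm within each cohort leaves the error across two independent cohorts at up to 1 − 0.95² = 9.75%. The same is true of Bonferroni within each cohort, so this does not favour either rule. It is a reason to state the family.

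**Conclusion.** The point holds as an avoidable inefficiency, not as a fault in validity. At the planned gain of 0.66, SD 1 and 131 per cohort, Holm over the six tests in a cohort adds 0 to about 9 points of power per responding subscale: none if one responds, about 3 points if three respond, and 8 to 9 points if all six respond at correlation 0 to 0.3. The main benefit is a fuller account of which subscales respond when several do.

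The error guarantee needs no assumption about dependence. The size of the power gain rests on the assumed number of responders and correlation, and should be reported as a range starting at zero. The claim that Holm never rejects fewer holds only when both rules use the same family.

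**What to change.** In the Protocol Summary (Primary Aim) and Section 11.0 (Primary Objective), before unblinding, state that significance for the primary aim is judged by Holm's step-down procedure at family-wise 0.05 over the six subscales within each cohort. This matches the family already written. Keep 0.05/6 only as the sizing figure.

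If the sponsor prefers one family of 12 tests across Cohorts 1 and 2, which the 131 would fit, say so, apply Holm over 12, and compare it with 0.05/12 rather than 0.05/6.

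The cost is one sentence in each place, with no extra participants or data and no loss of error control over the stated family. Confidence intervals that match Holm are less simple. Report Bonferroni intervals (99.17% for six tests, since 1 − 0.0083 = 0.9917), and note that one may include zero where Holm rejects, for example when p = 0.02 is reached at the 0.025 step.
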